Although the incidence of sternal complications after cardiac operations through median sternotomy is relatively low, ranging from 0.4% to 8%, it is associated with a comparatively high mortality rate of up to 47% if left undetected. Indicative of this, the 4-year survival rate of patients diagnosed with sternal complications is 65% compared with 85% in patients who heal without such complications [2]. Median sternotomy can have many complications like wound dehiscence and infection in 0.2 to 8 % of the patients [3, 4]. Some of the serious complications of sternotomy include Deep sternal wound problems DSWP following cardiac surgery, ranging from 0.4–3% in unselected patients [5]. DSWP are rare, but can have serious complications, as it is associated with prolonged hospital stays, long-term antibiotic therapy, multiple surgical procedures, higher mortality and morbidity, and increased patient suffering and costs [6]. This complication can be avoided by using protein rich plasma PRP, since platelets upon activation will excrete growth factors and attractants for tissue stem cells, thus promoting tissue healing [5].

The literature has identified a range of preoperative, perioperative, and postoperative risk factors that are suggested to contribute to the development of sternal complications [2] . Risk factors known for postoperative complications in patients going through cardiac surgery include obesity, bilateral harvesting of the internal mammary artery, unilateral LIMA harvesting, diabetes, steroid therapy, history of active smoking, osteoporosis, and chronic lung diseases [2, 7, 8, 9]. Two studies listed the postoperative requirement for blood products as an independent risk factor for sternal infection [2] . The replacement of blood products may lead to host immunosuppression and increase the risk of sternal infection [2] . Insulin-dependent diabetes mellitus is considered the most serious predisposing factor for deep infections [4]. Given that the IMA is a major blood supply to the sternum, some studies report mobilization of these arteries may lead to sternal hypoperfusion and increase the risk of sternal infection [2].

Complications in the post-surgery period are a significant source of mortality. Treatment of these complications may cause prolonged hospitalization, prolonged antibiotic therapy, and

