Postoperative complications cause significant morbidity in post cardiac surgery patients. The PRP has been proposed in clinical trials to reduce the frequency of complications in patients undergoing median sternotomy for cardiac operative procedures. The purpose of our study is to evaluate whether there is any beneficial effect of use of PRP in addition to standard care after on pump CABG, cardiac surgery.

Research Question

Does application of PRP after CABG, cardiac surgery reduce the frequency of sternal wound complications?

Objective

To compare the complication rates of application of PRP in addition to standard sternal wound closure versus standard sternal wound closure alone.

Population

All consecutive patients of age 45 to 72, undergoing CABG, cardiac surgery with median sternotomy will be included in the study.

Intervention

Application of 6 mL of autologous PRP to sternum and soft tissue during sternal closure.

Comparison

The control group will undergo midline sternotomy with a sternal saw blade. The sternum will be closed with a simple interrupted or figure of eight stainless steel wire. The wounds will be closed in a layered manner with absorbable suture and dressed with Steri-Strips, gauze and paper tape. The study group will additionally receive 6 mL of autologous PRP applied to sternum and soft tissue during sternal closure.

Outcome

(i) Primary Outcome;

Primary outcome will be measured as frequency of sternal wound complications in terms of delayed healing, superficial infection, deep infections, and readmission rate including mediastinitis in 30-days period post-surgery.

(ii) Secondary outcome;

Secondary outcome will be the overall cost burden for the 30-days post-surgery period.

(iii) Other outcomes;

Other outcomes will be ICU stay (days), blood transfusions more than 4 units and platelets transfusions more than 4 units within 30 days.

OPERATIONAL DEFINITIONS

1-Cardiac Surgery: Cardiac surgery, also called heart surgery, involves surgical operations performed on the heart to correct life-threatening conditions. The surgery can be either open-heart surgery or minimally invasive surgery depending on the condition to be corrected.

2-PRP: Platelet-rich plasma (PRP) is defined as a portion of the plasma fraction of autologous blood having a platelet concentration above baseline.

3-Study Outcome

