Patients from 45 to 72 years of age, undergoing on pump CABG,

cardiac surgery with median sternotomy.

Patients who provide consent.

Exclusion criteria

- BMI less than **18.5** or more than **24.9**
- Bilateral harvesting of the internal mammary artery,
- Steroid therapy,
- Known Diabetic,
- Active smoker,
- Osteoporosis,
- Chronic lung disease,
- CPB time more than 72.5 minutes
- Platelet Rich Plasma cannot be obtained.
- Patients who are not candidates for blood bank donations.

Sample size

The sample size has been calculated by using WHO size calculator with the statistical assumptions as following:

(Level of significance = 5%), (Power of test = 80%), (Population standard deviation = 3.0)

(Anticipated population, rate of oedema and infiltration in prp group, P1= 18%)

Anticipated population, rate of oedema and infiltration in control group, P2= 44% Sample size comes out to be 49 cases in each study group and a total of 98 patients will be included in the study.

Sampling Technique

Participants will be recruited using non-probability consecutive sampling and randomly assigned to one of two groups.

Data Collection Procedure

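### The 80% power and the 98 patients are calculated for oedema and infiltration, which is not an outcome of this trial; for the actual primary outcome the power is unsupported, and low at the complication rates the protocol itself quotes

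*Protocol*

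**What the plan says.** Under Material and Methods, Sample size, the protocol lists its assumptions as "Level of significance = 5%), (Power of test = 80%), (Population standard deviation = 3.0", then gives the PRP rate as "Anticipated population, rate of oedema and infiltration in prp group, P1= 18" per cent. It continues: "Anticipated population, rate of oedema and infiltration in control group, P2= 44% Sample size comes out to be 49 cases in each study group", 98 in total.

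Under Outcome, the primary outcome is something else: "Primary outcome will be measured as frequency of sternal wound complications in terms of delayed healing, superficial infection, deep infections, and readmission rate", the last including mediastinitis, all over 30 days. The secondary outcome is cost. The other outcomes are ICU stay and transfusion of more than 4 units of blood or of platelets.

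The Introduction gives the only background rates in the document: 0.4% to 8% for sternal complications after median sternotomy, 0.4% to 3% for deep sternal wound problems in unselected patients, and "Median sternotomy can have many complications like wound dehiscence and infection in 0.2 to 8 % of the patients".

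Data Analysis compares categorical outcomes by chi-square or Fisher's exact test at p<0.05, with complete-case handling of missing data.

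**The concern.** Oedema and infiltration occurs only in the Sample size section. It is absent from the outcomes, the Operational Definitions and the variables listed under Data Analysis. The trial is therefore sized on a variable it does not plan to measure, and no rate or effect is stated for the outcome it does plan to measure. The control rate used, 44%, is more than five times the highest complication rate in the Introduction (44/8 = 5.5). The listed "Population standard deviation = 3.0" has no place in a comparison of two proportions, which suggests that the inputs were not assembled for this endpoint.

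An ethics committee and later readers are told that the trial has 80% power. If it does not, a non-significant result would be taken as evidence that PRP does not work, when the design had little chance of showing an effect.

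**Working it through.** **Inputs from the protocol.** Significance level 5%; power 80%; 18% with PRP and 44% in control; 49 per arm; chi-square or Fisher's exact test (Data Analysis); background rates up to 8% (Introduction).

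**Assumptions.** The test is two-sided (sidedness is not stated, but this reproduces the plan's figure, whereas one-sided gives 39). The relative risk is 18/44 = 0.41, carried over because the protocol gives no effect for its primary outcome.

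**1. The plan's own figure.** Pooled two-proportion formula, with p̄ = (0.18 + 0.44)/2 = 0.31:

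n = [1.960·√(2p̄(1−p̄)) + 0.842·√(p₁(1−p₁) + p₂(1−p₂))]² / (p₂−p₁)²

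= [1.960 × 0.6541 + 0.842 × 0.6277]² / 0.26²

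= (1.282 + 0.528)² / 0.0676 = 48.5, so 49 per arm.

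This matches. No standard deviation enters. Exact power at 49 per arm is 81% with uncorrected chi-square and 75% with Fisher.

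**2. The same 49 per arm at other control rates.** Power is found by enumerating all pairs of binomial counts and adding the probability of those with two-sided p<0.05 in favour of PRP. The mixed column uses Fisher when an expected count is below 5 and uncorrected chi-square otherwise; that switching rule is a convention, not in the protocol.

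| Control rate | PRP rate (×18/44) | Fisher | Chi-square | Mixed |
|---|---|---|---|---|
| 3% | 1.2% | 0.2% | 3% | 0.2% |
| 8% | 3.3% | 5% | 18% | 6% |
| 15% | 6.1% | 17% | 32% | 27% |
| 20% | 8.2% | 28% | 41% | 40% |
| 30% | 12.3% | 49% | 59% | 59% |
| 44% | 18% | 75% | 81% | 81% |

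**3. What 8% means in events.** Expected counts are 49 × 0.08 = 3.9 in control and 49 × 0.0327 = 1.6 with PRP.

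**4. The most favourable effect at 8%.** Suppose PRP removed every event. Fisher needs at least 6 against 0 (5 against 0 gives p = 0.056), and P(X ≥ 6) for 49 patients at 8% is 19.5%. Uncorrected chi-square needs 4 against 0, which has probability 56%.

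**5. Precision at 8% against 3.3%.** The 95% half-width for the risk difference is 1.96·√(0.08×0.92/49 + 0.0327×0.9673/49) = 0.091, or 9.1 percentage points. That is more than the whole control rate.

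**6. Size needed at 8% against 3.3%.** The formula in step 1 gives 372.4, so 373 per arm (746 in total) for 80% power.

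**The case against.** The best counter-argument is that 0.2% to 8% is not the rate of the primary outcome. Those figures cover sternal complications, dehiscence and infection. The primary outcome also counts wounds not healed within two weeks and readmissions related to the index surgery, and the protocol gives no rate for either. The case mix is also unsettled. The exclusion criteria remove most of the risk factors listed in the Introduction (diabetes, active smoking, BMI above 24.9, steroids, osteoporosis, chronic lung disease, bilateral mammary harvest), but the Data Collection Procedure speaks of including emergencies, reoperations and transplants, contrary to the on-pump CABG criterion. One therefore cannot say that the rate must lie at or below 8%.

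This stands, and it makes the 8% row conditional. It does not rescue the stated power: at 30%, nearly four times the highest quoted rate, power is at most 59%, and the protocol supports 44% for none of its outcomes. Data Analysis also lists the components as separate variables, and no component can be more frequent than a composite of them.

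A second objection is that Fisher's test gives the gloomiest figures and the protocol does not say when it applies. That is fair, so both tests are shown. Chi-square gives a much better figure for complete elimination (56% against 19.5%), but that is still short of 80%.

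Finally, this is not a slip in calculation. The arithmetic is correct; the endpoint and rates fed into it are not those of the trial.

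**Conclusion.** The concern holds, and the section must be corrected. The stated 80% power belongs to a 44% against 18% difference in a variable that is not a trial outcome, and nothing in the protocol supports it for sternal wound complications.

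If the control rate is near the protocol's upper figure of 8% and the relative risk is 0.41, power is about 5% to 18%, depending on the test. Over control rates of 15% to 30% it runs from 17% to 59%. It reaches 80% only at about 44%, and then only with uncorrected chi-square.

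These figures rest on a two-sided 5% test, the carried-over relative risk, and all 49 patients per arm being analysed. The stated size has no allowance for loss, although complete-case analysis is planned. The true rate of the primary outcome remains unknown from the document.

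**What to change.** Rewrite the Sample size section for the actual primary outcome.

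1. Say whether the primary outcome is one composite (any listed event within 30 days) or one named component, so that there is a single rate to plan on.
2. State the anticipated control and PRP rates for it, with a source.
3. Delete the oedema and infiltration rates and the standard deviation of 3.0. State that the test is two-sided and which test is used.
4. Restate the power that 98 patients give at those rates, preferably as a table over control rates from 8% to 44%.
5. If the expected rate is near 8% or lower, withdraw the 80% claim, describe the trial as a pilot or estimation study, and make the risk difference with an exact or Newcombe 95% confidence interval the main result.

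This costs protocol wording only and no extra patients; the stated power becomes less favourable. Should the sponsor prefer to keep 80% power at a low event rate, the trial would have to be much larger (373 per arm at 8% against 3.3%). That is a choice for the sponsor and is not needed to correct the text.

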The study protocol will be first submitted for approval to the hospital ethics committee and Advance Research committee. A written informed consent will be taken from all parents/ caretakers. The subjects fulfilling inclusion will be enrolled from Cardiac Center. Participants will be recruited using non-probability consecutive sampling and randomly assigned to one of two groups. The antibiotic prophylaxis will be given 60 min before incision. The preoperative antibiotics protocol and glycemic management protocol will be standard and will remain the same for all patients throughout the study. Patients will be given general anesthesia. This will ensure that they are asleep and pain free through the whole surgery. An incision of 8- to 10-inch will be made in the chest. A midline sternotomy with a sternal saw blade will be done. Bleeding sites will be secured followed by pericardectomy. Once the heart is visible, cannulation will be done and the patient will be connected to a heart-lung bypass machine. The machine will move blood away from the heart so that the surgeon can operate. Surgery will be performed according to local guidelines. Patients will be heparinized using an initial dose of 300 IU/kg unfractionated heparin. During surgery the activated clotting time (ACT) will be maintained at least 480 s. All patients undergoing sternotomy will be included in the study including emergencies, reoperations, ventricular assist device implantations, heart transplants, aortic dissections and standard operations (i.e. coronary artery bypass grafting and valve repairs or replacements). Following sternotomy, the use of bone wax on the sternum will be avoided, as this might form an intrasternal barrier and interfere with PRP augmented healing. Targeted flow rates during cardiopulmonary bypass were 2.6 L/min/m² , yielding a venous saturation of 70–80%. After heparin reversal is achieved with protamine, all the bleeding spots will be identified and stopped i.e. haemostasis will be secured. The control group will undergo midline sternotomy with a sternal saw blade. The sternum will be closed with a simple interrupted or figure of eight stainless steel wire. The wounds will be closed in a layered manner with absorbable suture and dressed with Steri-Strips, gauze and paper tape. The study group will additionally receive 6 mL of autologous PRP applied to sternum and soft

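### The Data Collection Procedure admits all sternotomy patients, including assist-device, transplant, dissection and valve operations, while the rest of the protocol restricts the trial to CABG

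*Protocol*

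**What the plan says.** The protocol describes its population in several places.

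- **Opening summary:** consecutive consenting patients having on-pump coronary bypass grafting through a sternotomy.
- **Rationale:** the evaluation of "any beneficial effect of use of PRP in addition to standard care after on pump CABG, cardiac surgery" is given as the purpose of the trial.
- **Research Question:** "Does application of PRP after CABG, cardiac surgery reduce the frequency of sternal wound complications".
- **Population:** "All consecutive patients of age 45 to 72, undergoing CABG, cardiac surgery with median sternotomy will be included in the study".
- **Inclusion criteria:** "Patients from 45 to 72 years of age, undergoing on pump CABG", with median sternotomy and consent. A list of exclusions follows, covering BMI, diabetes, active smoking, bypass time and "Bilateral harvesting of the internal mammary artery", among others.
- **Data Collection Procedure, near the start:** "The subjects fulfilling inclusion will be enrolled from Cardiac Center".
- **Data Collection Procedure, within the account of the operation:** "All patients undergoing sternotomy will be included in the study including emergencies, reoperations, ventricular assist device implantations, heart transplants, aortic dissections and standard operations". Standard operations are then explained as "coronary artery bypass grafting and valve repairs or replacements".

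**The concern.** The last of these statements is worded as an eligibility rule, not as a description of the department's workload: it says who will be in the study. It names operations that are not CABG, so it conflicts with the inclusion criterion and with the question the trial sets out to answer.

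Staff who follow that sentence would randomise assist-device, transplant, dissection and isolated valve patients. Staff who follow the Inclusion criteria would not. Randomisation still protects the comparison between arms, so the main harm is not bias. The harm is that the trial population is undefined, that some patients enrolled under one sentence would be ineligible under another, and that the result could not be tied cleanly to a question about PRP after CABG.

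**Working it through.** **The planned sample size, for reference.** The Sample size section gives 5% significance, 80% power, P1 = 0.18 and P2 = 0.44. It does not state sidedness; two-sided is assumed here. With the pooled two-proportion formula:

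- mean proportion = (0.18 + 0.44)/2 = 0.31, and difference = 0.26
- n = [1.960 × √(2 × 0.31 × 0.69) + 0.842 × √(0.18 × 0.82 + 0.44 × 0.56)]² / 0.26²
- n = [1.960 × 0.654 + 0.842 × 0.628]² / 0.0676 ≈ 48.5, rounded up to 49 per group

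This matches the stated 49 per group and 98 in total. Operation type does not enter the calculation, so the contradiction does not alter the figure.

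**The named items set against the inclusion criterion (on-pump CABG).**

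| Item in the Data Collection Procedure sentence | Against on-pump CABG |
|---|---|
| Coronary artery bypass grafting | In scope |
| Emergencies | Neutral: can be an on-pump CABG |
| Reoperations | Neutral: can be an on-pump CABG |
| Valve repairs or replacements | In scope only if combined with on-pump CABG |
| Ventricular assist device implantations | Outside as named |
| Heart transplants | Outside as named |
| Aortic dissections | Outside as named |

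Total: 1 + 2 + 1 + 3 = 7. Emergencies and reoperations are not part of the conflict, because nothing in the Exclusion criteria bars them.

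**Statements on the other side.** Five name CABG: the opening summary, Rationale, Research Question, Population and Inclusion criteria. The enrolment sentence in the Data Collection Procedure defers to the inclusion criteria and so sides with them.

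**Can both be followed?** Take a patient aged 60 having only a valve replacement, with none of the listed exclusions. The Inclusion criteria say no, because the operation is not CABG. The Data Collection Procedure sentence says yes. Neither statement is made subject to the other.

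**A wider reading.** Taken literally, the reference to all sternotomy patients would also set aside the age limits and the exclusions. Seven of the eight risk factors listed in the Introduction reappear as exclusions: obesity (through the BMI limit), bilateral mammary harvesting, diabetes, steroids, smoking, osteoporosis and chronic lung disease. On that reading the event rate could change. It is only one possible reading, and the conflict over operation type does not depend on it.

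**Scale.** One patient is 1/98 ≈ 1.0% of the trial, and one event moves the rate in an arm by 1/49 ≈ 2.0 percentage points. How many non-CABG patients would enter, and how often they would have events, cannot be derived from the protocol.

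**The case against.** The strongest reply is that eligibility has its own headed sections, that the Data Collection Procedure ties enrolment to them, and that the conflicting sentence sits inside the surgical narrative, between the clotting-time target and the instruction on bone wax. A careful reader would probably treat it as misplaced text. That is fair as a guess at intent, but no statement ranks the headed criteria above this sentence. It comes after the criteria, in the section staff work from. If it is left-over text, that is a reason to remove it.

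A second reply is that four of the five CABG statements pair CABG with the general term cardiac surgery, that the protocol defines cardiac surgery broadly, and that the Objective and Hypothesis do not mention CABG. The wording is indeed loose, and only the opening summary is free of it. But the Rationale and the Inclusion criteria both specify on-pump CABG. Reading the phrase as any cardiac operation would leave CABG with no function there, and the opening summary would still conflict.

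A third reply is that the bypass-time exclusion (above 72.5 minutes) would remove the other operations anyway. The protocol gives no bypass times by operation, so this cannot be shown, and a short isolated valve operation would still not be a CABG.

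Two points do stand. The item count describes the conflict but does not measure its effect, and treating valve surgery as conditional while calling three other operations outside as named is partly a matter of judgement. The event-rate consequence is speculative and should carry no weight in the decision to correct the text.

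**Conclusion.** The concern holds. The protocol contradicts itself on which operations make a patient eligible, and nothing in it resolves the contradiction. Three of the seven named items fall outside CABG as named, and a fourth does so unless combined with on-pump CABG. The sample size is unaffected, and no effect on the event rate or the treatment comparison can be quantified from the protocol.

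The conclusion rests on reading the loosely worded CABG statements as meaning CABG, which the opening summary, Rationale and Inclusion criteria support. It does not rest on the age limits or exclusions being overridden. The text needs correcting because it determines who is randomised and which population the result covers.

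**What to change.** Replace the sentence in the Data Collection Procedure with a reference to the Inclusion and Exclusion criteria. If CABG is the intended population, this is one sentence, with no cost in sample size or data collection. Tidying the CABG wording in the Research Question, Rationale, Population and Inclusion criteria at the same time would remove the remaining ambiguity.

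If a broad sternotomy population is really intended, the opening summary, Rationale, Research Question, Population and Inclusion criteria must be rewritten to say so, and the planning rates behind the sample size reviewed for that population. That is a larger change.

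The correction should be made before enrolment. If patients have already been randomised, the sponsor should also record which statement was applied and the operation type of each patient enrolled so far.
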